6.3 SUBJECT EARLY TERMINATION (WITHDRAWAL)

Any subject who wishes to voluntarily discontinue study drug or withdraw from participation in the study for any reason is entitled to do so without obligation. If a subject requests to discontinue the study drug, the subject will be withdrawn from the study as an Early Termination (see [Section 6.2.10](#)).

The Investigator may discontinue any subject from study drug or from study participation, if deemed necessary at any time during the study for any reason including, but not limited to:

- The investigator considers that the subject requires alternative medication that is incompatible with further continuation of the study drug or participation in the study.
- Occurrence of any medical condition or circumstance that exposes the subject to substantial risk and/or does not allow the subject to adhere to the requirements of the protocol.
- Any SAE, clinically significant AE, severe laboratory abnormality, intercurrent illness, or other medical condition that indicates to the Investigator that continued participation in the study is not in the best interest of the subject or that continued participation could affect study objectives.
- Any woman who reports becoming pregnant while participating in the study. Information on the pregnancy and outcome will be requested by the Investigator.
- Subject's continued failure to comply with protocol requirements or study-related procedures after being instructed on the correct requirements or procedures by the Investigator or site personnel.
- Termination of the study by the Sponsor, FDA, or other regulatory authority.

In the event that early termination/withdrawal of a randomized subject is necessary ('withdrawn' subject), the Investigator should make every attempt to complete the study assessments as described in [Section 6.2.10](#) as soon as possible.

The reason for early termination/withdrawal of a subject should be recorded in the source documents and entered in the eCRF.

Subjects who are terminated early from the study will not be replaced.

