9.4.2 Management

Investigators will use clinical judgment to determine when to rescue a subject using the guidance provided in [Section 9.4.1](#) and the appropriate rescue medication to use. Rescued subjects will stop study drug and will continue in the study, and will be assessed at each subsequent visit, if possible, through completion of the Visit 6 (POD22) assessments (if participating in the Main study) or Visit 7 (POD85) assessments (if participating in the Endothelial Cell Sub-study) (Table 1) or until the Investigator has deemed the subject is stable and can be released from the study.

If a subject needs to be rescued at Visit 5 (POD15), the Visit 5 (POD15) assessments (Table 1) should be completed before the subject is administered rescue medication.

Rescued subjects will be considered treatment failures, and the need for rescue medication will not be considered as an AE.

An AE occurring at the time of rescue will be recorded in the eCRF and will be followed by the Investigator to stabilization or resolution of the AE or the end of the study (whichever comes last).

If a subject is rescued, this event will be recorded in the eCRF (not as an AE). Medications used for rescue will be recorded in the ConMeds section of the eCRF, indicating that they were used for rescue.

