9.5.2 Management

Investigator will use clinical judgment to determine the appropriate IOP-lowering medication to use and when to withdraw study drug and procedures, in consultation with the Study Medical Monitor.

It is important to note that prostaglandin-based IOP lowering medications are prohibited in this study.

- After randomization and start of study drug, if a subject has an IOP > 30 mmHg the Investigator may commence non-prostaglandin-based IOP-lowering medication while continuing the study drug, with appropriate follow-up at the next planned visit or at an unscheduled visit. The subject may require assessment at an unscheduled visit at the investigator's discretion.
 - If the IOP is < 30 mmHg at the next visit, the subject may continue on study drug.
 - If at the next visit, the IOP remains > 30 mmHg while on IOP-lowering medication, then the study drug may be discontinued and alternative IOP-lowering medication

may be started, after consultation with the Study Medical Monitor. The subject should continue in the study and complete the assessments indicated in Table 1 through Visit 6 (POD22) (Main Study) or Visit 7 (POD85) (Endothelial Cell Sub-study). The Study Medical Monitor should discuss the persistent elevation of IOP with the Sponsor Medical Monitor.

- After randomization and start of study drug, an IOP of ≥ 21 mmHg AND an increase > 10 mmHg from the Visit 2 (POD1)/pre-dose baseline (both criteria must be met) is considered clinically significant and the Investigator should consider starting non-prostaglandin-based IOP-lowering medication while continuing the study drug, with appropriate follow-up at the next planned visit or at an unscheduled visit.
 - If the IOP reduction is satisfactory at the next visit, the subject may continue on study drug.
 - If the IOP reduction of IOP is not satisfactory at the next visit, then the study drug may be discontinued and alternative IOP-lowering medication may be started, after consultation with the Study Medical Monitor. The subject should continue in the study and complete the assessments indicated in Table 1 through Visit 6 (POD22) (Main Study) or Visit 7 (POD85) (Endothelial Cell Sub-study). The Study Medical Monitor should discuss the persistent elevation of IOP with the Sponsor Medical Monitor.

Medications used for treating increased IOP will be recorded in the Concomitant Medications section of the eCRF, noting that they were used to reduce IOP.

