10.3.2 Analysis of Efficacy

All efficacy analyses and summaries will be based on assessments in the study eye for each subject.

Subjects who are rescued at any time prior to Visit 5 (POD15) will be considered as treatment failures for the primary efficacy endpoints and the relevant secondary efficacy endpoints. For subjects who discontinue from the study prior to Visit 5 (POD15), the last observation carried forward (LOCF) approach will be used to impute missing data.

For continuous secondary efficacy endpoints, the LOCF approach will also be used to impute the data at visits after subjects are rescued.

The ACC count will be graded as shown below:

Grade	0	1	2	3	4
ACC Count	0 cell	1-5 cells	6-15 cells	16-30 cells	> 30 cells

10.3.2.1 Analyses of Primary Efficacy Endpoints:

The primary efficacy analyses to compare APP13007 against placebo will be conducted on the ITT population using the Pearson Chi-square statistic. Fixed sequence testing will be employed to maintain the 2-sided alpha = 0.05. The primary analyses will first test the difference between treatments in the proportion of subjects with ACC count = 0 (Grade = 0) at POD8 (Visit 4) maintained through POD15 (Visit 5). If the test is statistically significant at the 2-sided alpha = 0.05 level in favor of APP13007, the difference between treatments in the proportion of

subjects with Ocular Pain grade = 0 at POD4 (Visit 3) maintained through POD15 (Visit 5) will be tested at the two-sided alpha = 0.05 level.

To confirm the robustness of primary analysis results, sensitivity analyses, including using observed data from all subjects, will be performed. The detailed sensitivity analyses will be described in the SAP.

10.3.2.2 Analyses of Secondary Efficacy Endpoints:

Mean change-from-baseline in ACC Grade, ocular Pain Grade, ACF Grade and visual acuity at PODs 4, 8 and 15 will be analyzed using an analysis of covariance (ANCOVA). The ANCOVA model will include treatment as a fixed effect and baseline as a covariate. The rest of secondary efficacy endpoints will be analyzed using the same method described for the primary efficacy endpoints.

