6.4.3 Handling Dropouts or Missing Data

6.4.3.1 Imputation of Missing Efficacy Data

The missing data handling rule for the study eye will be applied for the efficacy endpoints.

Missing data from subjects who discontinue the study before POD15 assessments without taking rescue medication:

For subjects who prematurely discontinue the study without taking rescue medication, the LOCF approach will be used to impute the missing data. The last observation will be the last assessment value after the first dose of study drug and up to two days following the last dose of study drug.

Missing data from subjects who discontinue the study before POD15 assessments and take rescue medication before POD15 assessments:

For both categorical and continuous secondary efficacy endpoints of ACC grade, ocular pain grade and ACF grade, subjects who take rescue medication before POD15 assessments and prematurely discontinue the study, the LOCF approach will be used to impute the missing data. The last observation will be the last assessment value after the first dose of study drug and prior to starting rescue medication.

Intermittent missing data:

The likelihood of having intermittent missing data is low. For subjects with intermittent missing data for efficacy endpoints, the LOCF approach will be applied to impute the missing data, i.e., using the data collected from the most recent prior visit after the first dose of study drug.

If no data can be carried forward (i.e., missing assessments at POD 4 visit or no available post-baseline assessments), missing data will be treated as missing for the continuous endpoints and will be considered as 'Non-responder' for the categorical endpoints.

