10.1.4 Additional Analysis

The primary efficacy endpoints will be analyzed using the data collected up to POD15. The rescued subjects will not be considered as treatment failures (Non-responders) for this analysis. All subjects' data collected up to POD15, including the data from subjects who take rescue medication, will be used to analyze the primary efficacy endpoints. Only observed data will be included to derive the primary efficacy endpoints. For the primary endpoint of ACC grade, subjects who miss one of POD 8 and POD15 assessments will be considered as treatment failures (Non-responders). For the primary endpoint of ocular pain grade, subjects who miss one of PODs 4, 8 and 15 assessments will be considered as treatment failures (Non-responders). The Pearson's Chi-square test will be used to test the treatment difference.

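### A subject who only asks to stop study drug is withdrawn from the study, while rescued and IOP-stopped subjects stay, so obtainable outcomes and safety follow-up are lost

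*Protocol*

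**What the plan says.** **Subject asks to stop drug.** Protocol 6.3 opens by treating stopping drug and leaving the study as two different choices, then merges them: "If a subject requests to discontinue the study drug, the subject will be withdrawn from the study as an Early Termination". Under 6.2.10 the subject has the Visit 6 assessments at or soon after exit, and no further scheduled visits. No other section keeps this subject in follow-up.

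**Rescue.** Protocol 9.4.2: "Rescued subjects will stop study drug and will continue in the study, and will be assessed at each subsequent visit, if possible". Sections 5.4.1 and 6.2.12 agree.

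**Drug stopped for persistent IOP elevation.** Protocol 9.5.2: "The subject should continue in the study and complete the assessments indicated in Table 1", through Visit 6 or Visit 7.

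**Other signs that the two events are distinct.** Protocol 5.1.2.1 has the bottle of a subject who discontinues drug collected at the next clinic visit. SAP 7.1 tabulates drug discontinuation and study discontinuation separately.

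**Analysis.** The primary analysis is on the ITT population (Protocol 10.3.2.1). SAP 6.4.3.1: "For subjects who prematurely discontinue the study without taking rescue medication, the LOCF approach will be used to impute the missing data". The value carried forward may come from up to two days after the last dose; if there is none, the subject is a non-responder. SAP 6.3.5 excludes efficacy assessments made more than two days after the last dose when fewer than 14 days of drug were taken. In SAP 10.1.4 all data to POD15, "including the data from subjects who take rescue medication, will be used to analyze the primary efficacy endpoints"; a subject missing a required visit is a non-responder.

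**The concern.** Of the routes off drug, the subject's own request is the one that removes a person who may be content to keep attending. Both primary endpoints are sustained responses: ACC needs POD8 and POD15, and pain needs POD4, POD8 and POD15. A subject who leaves early may have no value at one or more of these visits.

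The plan then assigns outcomes by rule, and the rules can disagree. Take a subject with zero cells at POD8 who asks to stop the next day and is not rescued. LOCF makes this subject a sustained responder with no POD15 observation; SAP 10.1.2 has a category for responders with imputed data. SAP 10.1.4 makes the same subject a non-responder. A true POD15 value could have been observed.

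Reasons for stopping, such as poor tolerability or already feeling well, can relate to outcome and can differ by arm. Safety is affected too. For a withdrawn subject the end of the Main Study is the Early Termination visit (SAP 6.3.4), and the treatment-emergent window closes there (SAP 11.2). Scheduled IOP measurement to POD22 is lost, as is the POD85 endothelial measurement for a Sub-study subject.

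**Working it through.** **1. The plan's own figures** (Protocol 10.4, SAP 4). Inputs: ACC 26% v 12%, pain 57% v 38%, two-sided 5%, 175 per arm, 5% dropout. Using the pooled-variance formula without continuity correction,

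power = Φ{ [ |p1−p2|√n − 1.96√(2p̄(1−p̄)) ] / √(p1(1−p1)+p2(1−p2)) }.

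- ACC, n = 175: (1.852 − 1.087)/0.546 = 1.40, so power is 91.9% (stated 92%). Solving for n at 92% gives 176 (stated 175).
- Pain, n = 175: 94.8% (stated 95%).
- Dropout: 175/0.95 = 184.2, rounded up to 185.

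The stated figures reproduce. With every outcome known on 185 per arm, power is 93.3% (ACC) and 95.8% (pain).

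**2. Effect where a missing visit means non-response (SAP 10.1.4).** The documents give no rate for subject-requested stops, so the share w per arm is an assumption. Suppose these subjects would have responded at the planned rates and all become non-responders. Each rate is then multiplied by (1 − w), and so is the difference.

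| w | ACC difference (points) | ACC power | Pain difference (points) | Pain power |
|---|---|---|---|---|
| 0 | 14.0 | 93.3% | 19.0 | 95.8% |
| 1% | 13.9 | 93.0% | 18.8 | 95.5% |
| 2% | 13.7 | 92.7% | 18.6 | 95.2% |
| 5% | 13.3 | 91.7% | 18.05 | 94.0% |
| 10% | 12.6 | 89.9% | 17.1 | 91.7% |

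At 5% (0.05 × 185 = 9.25 per arm), ACC is 24.7% v 11.4%. The 5% row credits the entire all-cause dropout allowance to this one rule.

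**3. Would retained visits reach the primary analysis?** Mostly not. A subject who stops drug before 14 days and attends later visits produces values more than two days after the last dose, which SAP 6.3.5 excludes. LOCF would still supply most of the primary result.

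**4. Would they reach SAP 10.1.4?** By its purpose, yes; by its wording, this is unclear. SAP 10 applies the Analysis Visits of 6.3.5 to the efficacy analyses, and 10.1.4 does not say that the two-day rule is lifted. Rescued subjects also stop drug, so applying that rule would remove much of the post-rescue data that 10.1.4 sets out to use. The intention can be inferred but should be written down.

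**The case against.** The strongest case against is that the group is small and the plan already handles it.

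- Lack of efficacy, including pain that does not improve, is a rescue route (Protocol 9.4.1), and persistent IOP elevation is covered by 9.5.2. Both keep the subject in the study. This narrows the group but does not empty it: rescue is discretionary, and tolerability or inconvenience has no matching provision.
- A subject with pain at POD4 or cells at POD8 has already failed that endpoint, so POD15 adds nothing. The exit visit includes pain and slit-lamp assessment and can supply a value if it falls in a window and within two days of the last dose. Both points stand: not every such subject lacks a determinable outcome.
- SAP 10.1.3 has completer and observed-case analyses, and 10.1.2 shows imputed responses separately. These reveal the gap without filling it. The tipping-point analysis runs only if more than 5% of data are missing in an arm and significance is claimed, and it moves only imputed placebo non-responders.
- Collection of the bottle at the next clinic visit could mean the exit visit, so Protocol 5.1.2.1 is supporting evidence only.
- Protocol 8.4 provides for follow-up of unresolved adverse events after release. What is lost is the scheduled assessments and the capture of new events.

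A reader might go further and infer that the rule could move the primary result by many points: 9/185 = 4.9 points per arm, or 9.7 points on the difference if the arms are set to opposite extremes. At exactly 5% per arm, those extremes put the ACC difference between 24.7 − 16.4 = 8.3 and 29.7 − 11.4 = 18.3 points. The documents do not support that reading. The 5% is all-cause, the two arms would have to go wholly opposite ways, and an all-success assignment cannot arise in SAP 10.1.4. In the primary analysis, SAP 6.3.5 means that retaining these subjects would change little.

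**Conclusion.** The inconsistency is real. Protocol 6.3 removes subjects whom 9.4.2 and 9.5.2 would keep had they come off drug for rescue or IOP. The cost is observable POD8/POD15 outcomes for SAP 10.1.4 and scheduled safety follow-up to POD22 or POD85.

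The numerical effect is modest. Even with the full 5% attributed to this rule, response at the planned rates and every such subject scored as a failure, the ACC difference falls by 0.7 points and ACC power is 91.7%, against 92% planned. The actual share is unknown. The weight of the point is bias and interpretability: the primary and additional analyses can assign opposite assumed outcomes to the same subject when a real one was available. It does not show that the primary analysis is invalid or underpowered.

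**What to change.** **Protocol 6.3.** State that a subject who asks to stop study drug but does not withdraw from participation is asked to continue the scheduled assessments through Visit 6 (Visit 7 in the Sub-study). Reconcile this with 5.1.2.1, 9.4.2 and 9.5.2. Leave unchanged the subject's right to withdraw, the investigator's withdrawal grounds in 6.3, 9.1.1.3 and 9.1.1.4, and every rule on when drug is stopped.

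**SAP 10.1.4.** Add one sentence saying that off-drug observations up to POD15 are used in this analysis despite the two-day rule in SAP 6.3.5, which continues to govern the primary analysis. Without it, the protocol change might not reach any efficacy analysis.

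**Cost.** A protocol wording amendment, one SAP sentence, and a few visits that are already scheduled. The sample size and primary test do not change.

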6.4 STUDY DISCONTINUATION CRITERIA

6.4.1 Early Discontinuation of the Study

The study or parts of the study may be discontinued by the Sponsor or at the recommendation of the Investigator after consultation with the Sponsor. This may be based on a significant number of AEs of a similar nature that warrant such action.

6.4.2 Discontinuation of a Study Site

The Sponsor may discontinue the study at a site for reasons that include GCP violations, protocol deviations, lack of enrollment or for the protection of the safety and wellbeing of a subject.

7.0 STUDY ASSESSMENTS AND PROCEDURES

7.1 DEMOGRAPHY AND MEDICAL HISTORY

Subjects' demographic information will be collected and recorded in the eCRF. A complete systemic and ocular medical and surgical history will be taken at screening, and abbreviated assessment will be taken at the subsequent visits.

7.2 EFFICACY ASSESSMENTS

7.2.1 List of Efficacy Assessments

The ocular efficacy assessments apply to the Study (Operated) Eye Only.

- Slit Lamp Biomicroscopy assessment of (i) ACC count and (ii) ACF grade using a 5 point scale (0-4).
- Subject-Rated Ocular Pain Assessment (0-4 Scale)
- Number of subjects who are rescued
- Best corrected visual acuity by pinhole method using an ETDRS chart

7.2.2 Procedures for Assessment of Efficacy Endpoints

7.2.2.1 Anterior Chamber Cell Count and Anterior Chamber Flare

The biomicroscopy examination will be performed with the slit lamp using a slit-beam. The Investigator should use their usual examination technique. Anterior chamber cells should be counted using the high light intensity level and the high magnification (Haag-Streit 16 X or comparable), with the slit beam set at an oblique angle, and the height and width of the beam set to 1.0 X 1.0 mm.

ACF will be graded as shown below:

Grade	Description
0	None
1	Faint
2	Moderate (iris and lens details clear)
3	Marked (iris and lens details hazy)
4	Intense (fibrin or plastic aqueous)

7.2.2.2 Subject-Rated Ocular Pain Assessment

Ocular pain is defined as throbbing, or aching, and will be graded by the subject on a 5-point scale. At the visits shown in Table 1, subjects will be required to subjectively rate their pain in the study eye before any other ocular assessments are performed.

Ocular Pain will be graded a shown below:

Grade	Description
0	None: No pain.
1	Minimal: Presence of minimal throbbing or aching pain (expected following cataract surgery).
2	Mild: Presence of mild throbbing or aching pain, easily tolerated.
3	Moderate: Presence of moderate throbbing or aching pain leading to the desire to use an analgesic.
4	Severe: Presence of severe throbbing or aching pain that is not tolerable

7.2.2.3 Best corrected Visual Acuity

The assessment of best corrected visual acuity in the study (operated) eye will be performed as described in [Section 7.3.1.2](#).

7.3 SAFETY ASSESSMENTS

The safety assessments are applied to both eyes at Visit 1 (Screening) and Visit 6 (POD22) or Early Termination/Withdrawal or to the Study (operated) eye only at Visit 2 through Visit 5 (Table 1 Schedule of Events). The safety assessments in Table 1 are not performed on the day of surgery.

In the Endothelial Cell Sub-study, the corneal endothelial cell parameter measurements are performed in both the planned study eye and non-study eye at Visit 1 (Screening), and in the study eye only at Visit 6 (POD22)/Early Termination and Visit 7 (POD85).

7.3.1 List of Safety Assessments

- AEs
- ETDRS Assessment of Best Corrected Visual Acuity by Pinhole Method
- Slit Lamp Biomicroscopy assessment of the following signs of inflammation: corneal edema, ciliary flush, bulbar conjunctival injection. The assessments in the non-study eye will include an assessment of the lens
- IOP Measurement using Goldmann applanation tonometry
- Dilated Ophthalmoscopy assessment of the vitreous, retina, macula, choroid, and optic nerve with cup/disc ratio, and an assessment of the presence and severity of a cataract if present in the non-study eye
- Corneal Endothelial Cell Parameters: corneal endothelial cell density (cells/mm²), percent hexagonality and coefficient of variation (only in Endothelial Cell Sub-study)

7.3.1.1 Assessment of Adverse Events

All AEs spontaneously reported by the subject or in response to an AE query from study personnel or revealed by observation, physical examination or other diagnostic procedures will be recorded in the source document and on the appropriate pages of the eCRF. Any clinically relevant deterioration in a clinical finding is considered an AE and must be recorded. When

possible, signs and symptoms indicating a common underlying pathology should be noted as one (1) comprehensive event. Any pre-existing medical condition that worsens after administration of study drug will also be considered as an AE.

Ocular complaints associated with and expected as a result of the surgery, that are not recorded as AEs in the eCRFs will be recorded in the source documents. An ocular complaint will be recorded in the eCRF as AE when the complaint is outside the normal limits for cataract surgery or is associated with clinical sequelae (i.e., adverse slit lamp examination finding).

See [Section 8.0](#) for information on how to record AEs and how to attribute relatedness of an AE to study procedures, cataract surgery or study drug.

